Name of Active Ingredient

L-threonyl-L-prolyl-L-prolyl-L-threonine amide, acetate salt

schedule defined by treatment plan set by the investigator.

Rapastinel (GLYX-13) will be administered. Subjects will remain in the study unit until determination by the investigator that they are medically able to leave the study unit.

At the last visit of each quarter, the

ECG will be recorded and blood and urine samples will be obtained for laboratory analysis. Rapastinel (GLYX-13) will be administered. Subjects will remain in the study unit until determination by the investigator that they are medically able to leave.

Dose Level

Unit doses of rapastinel (GLYX-13), 225 mg/3 mL or 450 mg/3 mL IV, will be administered in a "slow bolus" injection to each subject in an upper extremity vein within approximately 1 to 2 minutes. Investigator will begin treatment based on the dose level (5 mg/kg or 10 mg/kg) to which the subject was assigned during participation in GLYX13-C-202; subjects originally assigned to 5 mg/kg will receive 225 mg/3 mL, and subjects originally assigned to 10 mg/kg will receive 450 mg/3 mL. If subject experiences adverse event(s) that the investigator believes may be associated with rapastinel (GLYX-13), the investigator may decrease dose level from 450 mg to 225 mg. If at any point the patient cannot tolerate the minimum 225 mg unit dose, the patient should be discontinued from the study.

Dose Interval

Dose interval for the first month of participation will be that (weekly or biweekly) to which the subject was assigned during the randomized withdrawal phase of GLYX13-C-202. The investigator will then formulate a treatment plan in which dose interval will remain the same or change. The treatment plan may be modified from time to time by the investigator if it is deemed prudent based on subject's depression status.

Treatment Plan

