6.3 Treatment Plan

Following one month at the dose level (subjects who were assigned to placebo during the randomized withdrawal phase of GLYX13-C-202 are eligible to participate and will begin at the dose level to which the subject was assigned during the stabilization phase of GLYX13-C-202) and dose interval to which the subject was assigned during the randomized withdrawal period of GLYX13-C-202, the investigator may continue the same dose level and dose interval, or may change the dose level and dose interval. The investigator will complete a treatment plan that outlines the dose level and dose interval at which rapastinel (GLYX-13) will be administered. The investigator, at the investigator's discretion, may change the treatment plan to alter dose level and/or dose interval based on the subject's depression status.

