8.4 Dose Interval

Dose interval for the first month of participation will be that (weekly or biweekly) to which the subject was assigned during the randomized withdrawal phase of GLYX13-C-202. The investigator will then formulate a treatment plan in which dose interval will remain the same or change. The treatment plan may be modified from time to time by the investigator if it is deemed prudent based on subject's depression status.

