12.7.1 Recording of Adverse Events

Subjects should be instructed to report all AEs to the investigator. AE collection begins at signing of ICF and ends 30 days after last dosing injection. In addition, the investigator should seek to elicit any clinical or objective reactions by specific questioning (eg, "How have you been feeling?") and, as appropriate, by examination. Information on all AEs should be recorded on the eCRF. All clearly related signs, symptoms, and results of diagnostic procedures performed because of an AE should be grouped together and recorded as a single diagnosis. The component parts of the diagnosis may be listed for verification. If the AE is a laboratory abnormality that is part of a clinical condition or syndrome, it should be recorded as the syndrome or diagnosis rather than the individual laboratory abnormality.

To avoid vague, ambiguous, or colloquial expressions, all AEs should be recorded in standard medical terminology on the eCRF and on the medical record rather than in the subject's own words. Each AE will also be described in terms of duration (start and stop date), severity, association with the study drug, action(s) taken, and outcome.

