12.8 Serious Adverse Events

An SAE is any AE occurring at any dose that results in any of the following outcomes:

Death

"Death" is an outcome and is NOT the AE. In the event of death, the cause of death should be recorded as the AE. The only exception is "sudden death" when the cause is unknown.

• Is a life-threatening experience

Life-threatening AEs include any adverse drug experience, which, in the view of the investigator, places the subject at immediate risk of death from the reaction as it

occurs. It does not include a reaction that, had it occurred in a more serious form, might have caused death.

- Requires inpatient hospitalization or prolongation of existing hospitalization
- Results in a persistent or significant disability/incapacity

Disability is defined as a substantial disruption in a person's ability to conduct normal life functions.

- Results in a congenital anomaly/ birth defect
- Additionally, important medical events that may not result in death, be life-threatening, or require hospitalization may be considered an SAE when, based upon appropriate medical judgment, they may jeopardize the subject and may require medical or surgical intervention to prevent one of the outcomes listed above. Example: allergic bronchospasm requiring intensive treatment in an emergency room or at home.

All SAEs that result in death or are life-threatening, regardless of causal relationship, must be reported to the medical monitor within 24 hours of the site's knowledge of the event. A copy of the initial SAE report must be received within one (1) business day.

All other SAEs or other events reportable to FDA and/or IRB will be forwarded to the medical monitor within one (1) business day.

The SAE report should provide as much of the required information as is available at the time. The following minimum information is required for reporting an SAE: subject identification, reporting source, and an event outcome. Supplemental information may be transmitted using a follow-up report and should not delay the initial report. The Sponsor will contact the investigational site to solicit additional information or to follow up on the event.

If there is any doubt whether the information constitutes an SAE, the information will be treated as an SAE for the purposes of this protocol. Serious adverse event collection will begin after signing the ICF and end 30 days after the last dose.

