9.1 ADVERSE EVENTS

AEs will be coded using the *Medical Dictionary for Regulatory Activities* (MedDRA).

An AE (classified by preferred term) will be considered a treatment emergent adverse event (TEAE) if it was not present before the first dose of study drug or was present before the date of the first dose of study drug and increased in severity during the study period till the end of participation. If more than 1 AE was reported before the first dose of study drug and coded to the same preferred term, then the AE with the greatest severity will be used as the benchmark for comparison with the AEs occurring during the study. An AE that occurs more than 30 days after the date of the last dose of study drug will not be considered as a TEAE. An AE that becomes serious on or after the first dose of study drug will also be considered as TEAE.

The number and percentage of subjects reporting TEAEs will be tabulated by SOC and preferred term and further categorized by severity and causal relationship to study drug. If more than 1 AE is coded to the same preferred term for the same subject, the subject will be counted only once for that preferred term using the greatest severity and strictest causality for the summarization by severity and causal relationship. The distribution of TEAEs by severity and relationship to study drug will be summarized. An AE that occurs more than 30 days after the date of the last dose of study drug will not be summarized.

The incidence of common (in \geq 2% of subjects) TEAEs during the study period till the end of participation will be summarized by preferred term and will be sorted by decreasing frequency.

An SAE that occurred between the date of the first dose of study drug and 30 days after the date of the last dose of study drug, inclusive, will be considered a treatment-emergent SAE (TESAE). The number and percentage of subjects who have TESAEs will be summarized by preferred term. In addition, the incidence of on-therapy SAEs that led to death will be summarized separately by preferred term.

The incidence of TEAEs leading to premature discontinuation of study drug during the study period till the end of participation will be summarized by preferred term, and will be sorted by decreasing frequency.

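### The treatment-emergent window closes 30 days after the last injection, so if the final dose interval is longer than that, whether a late event is tabulated depends on whether the subject was redosed

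*SAP*

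**What the plan says.** **The cut-off.** Under SAP 9.1 an AE that "occurs more than 30 days after the date of the last dose of study drug will not be considered as a TEAE". The same section adds: "An AE that occurs more than 30 days after the date of the last dose of study drug will not be summarized". Its TESAE definition also ends 30 days after the last dose.

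**Collection.** Protocol 12.7.1: "AE collection begins at signing of ICF and ends 30 days after last dosing injection". Protocol 12.8: "Serious adverse event collection will begin after signing the ICF and end 30 days after the last dose".

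**Dose interval.** Protocol 8.4: "Dose interval for the first month of participation will be that (weekly or biweekly) to which the subject was assigned" in the randomized withdrawal phase of the preceding study. It continues: "The investigator will then formulate a treatment plan in which dose interval will remain the same or change". Under Protocol 6.3 the investigator "may change the treatment plan to alter dose level and/or dose interval based on the subject's depression status". Neither section gives a maximum. The Synopsis supplies an indirect bound, since at the last visit of each quarter "ECG will be recorded and blood and urine samples will be obtained for laboratory analysis. Rapastinel (GLYX-13) will be administered". SAP Table 14.2-2 places those visits 91 days apart.

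**Endpoint period.** Protocol 5.1 and SAP 3.1 count subjects with an AE across the whole study. SAP 9.1 also refers several times to a period running to the end of participation. Neither period is tied to the last dose.

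**The concern.** A 30-day tail covers the whole of a weekly or biweekly interval, but that schedule is guaranteed only for the first month. Suppose a subject on a 6-week interval has an event 35 days after an injection. If the next injection is given, the last dose moves later and the event is a TEAE. If the event ends treatment, the last dose stays where it was, and the same event falls outside TEAE status and outside every AE summary.

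Inclusion thus depends on something that happens after the event and that the event can itself prevent. The error has one direction: counts can fall but not rise. It bears most on the TESAE table and the table of TEAEs leading to premature discontinuation, where single events matter and which exist to show this kind of event. It bears less on the primary count of subjects with any AE. The stated objective is the safety of long-term repeat exposure, with no restriction to acute effects.

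**Working it through.** The plan is descriptive and states no power, alpha or effect size, so it has no figure to reproduce. The check is arithmetic on the windows.

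**Inputs from the documents**
- Window after the last dose: 30 days (SAP 9.1; Protocol 12.7.1 and 12.8).
- Month 1 intervals: 7 or 14 days (Protocol 8.4, reading biweekly as every two weeks; twice a week would be shorter and change nothing).
- Implied ceiling: about 91 days (Synopsis dosing at the last visit of each quarter; 91-day spacing in SAP Table 14.2-2).

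**Assumed inputs:** interval lengths between 14 and 91 days. The documents give none.

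**Step 1. Uncovered part of a final interval of length I.** Uncovered days = max(0, I − 30); share = uncovered days / I. The last two columns divide the same days by 364 and by 1820 days, the end of year 1 and of year 5 in SAP Table 14.2-2.

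| I (days) | Uncovered days | Share of final interval | Share of 364 days | Share of 1820 days |
|---|---|---|---|---|
| 7, 14, 28, 30 | 0 | 0% | 0% | 0% |
| 42 | 12 | 12/42 = 29% | 3.3% | 0.7% |
| 56 | 26 | 26/56 = 46% | 7.1% | 1.4% |
| 91 | 61 | 61/91 = 67% | 16.8% | 3.4% |

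**Step 2. Chance of an event in the uncovered days.** With a constant AE rate r per subject-year, the chance of at least one is 1 − exp(−r × uncovered days / 365.25). The rates are assumptions.

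| I (days) | r = 0.5 | r = 1 | r = 2 | r = 4 |
|---|---|---|---|---|
| 42 | 1.6% | 3.2% | 6.4% | 12.3% |
| 56 | 3.5% | 6.9% | 13.3% | 24.8% |
| 91 | 8.0% | 15.4% | 28.4% | 48.7% |

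**Step 3. Effect on the primary count.** A subject drops out of the any-AE count only if no AE was counted earlier. With the last dose at day T and a 91-day interval, the chance is exp(−r(T + 30)/365.25) × [1 − exp(−61r/365.25)]. For r = 1 and T = 182 this is 0.560 × 0.154 = 0.086. Suppose 30 of 100 subjects are on 91-day intervals, are never redosed, and stay enrolled through the uncovered days. The expected number missing is:

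| Last dose (T) | r = 0.5 | r = 1 | r = 2 | r = 4 |
|---|---|---|---|---|
| Day 91 | 2.0 | 3.3 | 4.4 | 3.9 |
| Day 182 | 1.8 | 2.6 | 2.7 | 1.4 |
| Day 364 | 1.4 | 1.6 | 1.0 | 0.2 |

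These figures scale with the assumed fraction; at 10 subjects rather than 30 they are a third as large.

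**Step 4. After the fix.** With the window ending at the later of 30 days after the last injection and the termination visit, uncovered on-study days are 0 for every interval.

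**The case against.** **A reader might infer that these events are lost altogether because collection has closed. The documents do not support that.** At day 35 of a 6-week interval the next injection is still planned. The site learns that the earlier injection was the last only once the subject stops, so it has no reason to treat collection as over. Protocol 12.7.1 has subjects report all AEs, and the event would ordinarily be recorded. The listings at the end of SAP 9.1 cover SAEs, AEs leading to discontinuation and deaths with no stated 30-day limit. SAP 5.0 tabulates reasons for premature discontinuation, and Protocol 10.2 includes adverse event among them. This objection stands and limits the point to the summary tables. A narrower case remains: if the decision to stop comes first and an event follows after day 30 but before the termination visit, the collection rule does not require it to be recorded.

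**A reader might also infer that the interval is unlimited.** Dosing at the last visit of each quarter implies about 91 days, hence a nominal gap of about 61 days. Most of Protocol 9 and the schedule of evaluations cannot be read and may hold a tighter limit or a follow-up rule.

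**The premise may be rare.** The only intervals named are weekly and biweekly, and the SAP 14.2 visit windows are weekly. Protocol 4 reports that the effect of a single dose lasted 7 days but not 14. Nothing shows that intervals above 30 days are common. This stands as a limit on size.

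**Thirty days is generous pharmacologically.** With a half-life under 10 minutes, it spans at least 30 × 24 × 60 / 10 = 4,320 half-lives, and the two documents agree on it. This is a fair defence for acute effects, but it does not answer the asymmetry or the mismatch with an endpoint counted across the whole study.

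**Conclusion.** The point holds in a limited form. As written, SAP 9.1 makes tabulation of an event more than 30 days after an injection conditional on redosing, and the resulting error can only be downward. It requires a final interval above 30 days, which the readable text permits but does not report; at 30 days or less there is no bias.

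On the nominal schedule the gap is at most about 61 days. The effect on the primary any-AE count is small: about 1.4 to 2.7 of 100 subjects in the day-182 illustration, and 0.2 to 4.4 across all the cases shown. Those figures rest on assumed rates, an assumed 30% on quarterly dosing, and continued enrolment through the gap. The TESAE and discontinuation-TEAE tables are the more exposed, because a single omitted event can matter there. A claim that the primary endpoint is materially biased would go beyond what the documents show. This is a cheap improvement to the tabulation rule, not a flaw that undermines the study.

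**What to change.** **SAP 9.1.** End the TEAE, TESAE and AE-summary window at the later of 30 days after the last injection and the termination visit. Add a derived flag for events more than 30 days after the preceding injection, and show the affected counts with and without flagged events. This can be done alone for events already recorded.

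**Protocol 12.7.1 and 12.8.** Align the end of AE and SAE collection with the same rule at the next amendment.

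**Cost.** In the SAP: a few sentences, one flag, an extra column or footnote in the affected tables, and an entry in SAP 15.0 if the window then differs from the protocol. The protocol change needs an amendment sent to the IRB under Protocol 15.6, which is why it can wait for one made for other reasons. The downside is that a few events remote from the last injection enter the TEAE count; the flag keeps them visible and separable. No change to dosing is proposed.

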3.0 OBJECTIVES

3.1 PRIMARY OBJECTIVE

The primary objective of this study is to examine the safety of long-term repeat exposure to rapastinel (GLYX-13) in subjects who participated in GLYX13-C-202.

The primary endpoint of this study is to examine the number of subjects who experience an AE over the course of the study.

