4.1 SAFETY POPULATION

The Safety Population will consist of all subjects who received any injection of study drug. All safety analyses will be based on this population.

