7.1 EXTENT OF EXPOSURE

Exposure to rapastinel for the Safety Population will be summarized descriptively overall for treatment duration, calculated as the number of days from the date of first study drug taken to the date of last dose taken, inclusively. Subject-years, calculated as the sum of the treatment durations of all subjects divided by 365.25, will also be presented overall similarly using descriptive statistics.

Quarterly dose and overall quarterly dose of study drug will also be summarized overall using descriptive statistics. Quarterly dose for a subject is defined as the total doses taken during 1 quarter interval. Overall quarterly dose for a subject is defined as the total doses divided by total number of quarters over the treatment period.

[figure not shown]

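### SAP 9.1 summarises adverse events only over the whole study, with no rate per time at risk and no split by time on treatment, so it cannot show whether risk changes with continued dosing

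*SAP*

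**What the plan says.** SAP 3.1 makes the safety of long-term repeated dosing the primary objective and adds: "The primary endpoint of this study is to examine the number of subjects who experience an AE over the course of the study". Participation has no fixed length. Under Protocol 6.4 it ends with US approval, the subject's own exit or a sponsor decision to stop. The last window in SAP Table 14.2-2 closes on Day 1865 (1865/365.25 = 5.1 years). At the other extreme, SAP 4.1 says: "The Safety Population will consist of all subjects who received any injection of study drug". One dose is therefore enough.

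For adverse events, SAP 9.1 says: "The number and percentage of subjects reporting TEAEs will be tabulated by SOC and preferred term". A subject counts once per preferred term. TESAEs are given as number and percentage, TEAEs leading to discontinuation as incidence, and common TEAEs as those in at least 2% of subjects. One more line reads: "The distribution of TEAEs by severity and relationship to study drug will be summarized". It does not say whether subjects or events are counted, but it has no rate or time split either. The section also sets a counting window that opens at the first dose: "An AE that occurs more than 30 days after the date of the last dose of study drug will not be considered" treatment-emergent. It closes with listings of subjects with SAEs, with AEs leading to discontinuation, and of deaths.

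SAP 7.1 adds: "Subject-years, calculated as the sum of the treatment durations of all subjects divided by 365.25, will also be presented overall". Treatment duration there is "calculated as the number of days from the date of first study drug taken to the date of last dose taken, inclusively". No visible adverse-event summary uses these subject-years.

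**The concern.** When follow-up ranges from one injection to about five years, the percent of subjects with an event mixes two things: how risky the treatment is and how long people stayed. It also pools early and late events. A study meant to describe long-term safety should let a reader see whether events become more or less frequent as treatment continues. The planned tables give one pooled percent, which is the same whether risk falls or rises over the years. The same mixing affects the 2% cut-off for common TEAEs, since the underlying rate that reaches 2% depends on follow-up.

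**Working it through.** The plan states no event rate, length-of-stay distribution or precision target, so there is no figure to reproduce. Inputs from the documents are N up to 100 (SAP 12.0) and follow-up to about 5 years (SAP Table 14.2-2). All rates and stays below are assumptions for illustration, and a trial will have only one stay distribution.

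**1. Percent against time.** With constant first-event rate λ per subject-year, percent = 1 − exp(−λt).

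| λ | 6 months | 1 year | 3 years | 5 years |
|---|---|---|---|---|
| 0.5 | 22% | 39% | 78% | 92% |
| 1 | 39% | 63% | 95% | 99.3% |
| 2 | 63% | 86% | 99.8% | about 100% |

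The rate at which 2% of subjects are affected is −ln(0.98)/t: 8.1 per 100 subject-years at 91 days, 0.41 at 1820 days.

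**2. Two hypothetical stays, same risk.** Take exponential stay with pre-cap mean m, capped at 5 years. Mean stay = m(1 − exp(−5/m)), so m = 0.5 gives 0.50 years and m = 4 gives 2.85. With μ = 1/m, percent = λ/(λ+μ) × (1 − exp(−5(λ+μ))).
- λ = 1: 33.3% and 79.8%.
- λ = 0.05: 2.4% and 12.9%.

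**3. Dividing by SAP 7.1 subject-years.** This time runs to the last dose and does not stop at the first event. Per 100 subject-years, for the shorter and longer stay:

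| True rate | Events to last dose | Events to last dose + 30 days |
|---|---|---|
| 100 | 66.7, 28.0 | 77.2, 28.5 |
| 5 | 4.9, 4.5 | 5.7, 4.7 |
| 2 | 2.0, 1.9 | 2.3, 2.0 |

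The crude rate is fair for rare events and far off for frequent ones.

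**4. Change over time.** Yearly rates of 1.0, 0.4, 0.2 and of 0.2, 0.4, 1.0 both sum to 1.6, so both give 1 − exp(−1.6) = 79.8% at 3 years. By year, the incidence is 63/33/18% in one case and 18/33/63% in the other. No division by total subject-years separates them.

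**5. Early clustering.** Take 4 per year for 3 months, then 0.1. The percent is 52.9% for the shorter stay and 69.6% for the longer (ratio 1.3). The first-event rate on time at risk is 224 and 73 per 100 subject-years (ratio 3.1). A single overall rate then depends on stay more than the percent does.

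**6. First-onset tables and mixed risk.** Let half the subjects have rate 3 and half 0.3, all constant, with no dropout. The event-free fraction after 0 to 3 years is 1, 0.395, 0.276, 0.203. First onset is therefore 60/30/26% by year, although nobody's risk changes. The percent with any TEAE starting in the year is 60/60/60%.

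**7. Cell sizes.** For 100 subjects, numbers at the start of years 1 to 5 are 100·exp(−k/m) still followed, and 100·exp(−k/m − λk) still followed and event-free (k = 0 to 4).
- Longer stay, still followed: 100, 78, 61, 47, 37.
- Longer stay, event-free at λ = 1: 100, 29, 8, 2, 1; at λ = 0.05: 100, 74, 55, 41, 30.
- Shorter stay, still followed: only 14 and 2 enter years 2 and 3.

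Part-year follow-up lowers the yearly percent. At λ = 1 it is 57% (longer stay) or 32% (shorter) against 63% for a full year, from λ/(λ+μ) × (1 − exp(−(λ+μ))).

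**The case against.** The percent is what the endpoint asks for, the protocol synopsis rules out inferential analysis, and no comparator or test rests on the figure. That stands: the count contains no error.

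A reader might infer that SAP 9.1 ignores time altogether. The documents do not support this. It has a counting window tied to the first and last dose, and the windows in SAP 14.2 give time structure to visit-based safety data. What is absent is a rate or a time-specific summary of adverse events.

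A reader might also infer that no rate can be recovered. Step 3 shows otherwise for rare events. The same holds for TEAEs leading to discontinuation, where the event itself ends dosing. The listings also help with individual SAEs and discontinuations in a trial of at most 100 subjects, though they are not a summary.

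Some objections bear on the remedy, and they stand:
- An overall rate alone can depend heavily on stay (step 5).
- Years counted here are not years of exposure, because Protocol 7.1 requires 8 or more weeks of treatment in GLYX13-C-202. Dose interval may also change (Protocol 8.4), so calendar time is not a count of doses.
- SAP 14.8 can move a partly missing onset date to the first-dose date or to January 1, and so into another year.

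Parts of the SAP are not visible. The point is limited to the visible SAP 9.1, which reads continuously.

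**Conclusion.** The point holds as a limit on what the planned tables can show. The visible SAP 9.1 cannot show whether adverse-event risk changes with continued treatment, which is central to the stated objective. Under the assumed rates, opposite trends give the same 79.8%, and the same risk gives 33% or 80% depending on stay. Dependence on stay is weaker if events cluster early (53% against 70%). A crude rate from SAP 7.1 is serviceable for rare events (4.5 to 5.7 against 5) but not for frequent ones (28 to 77 against 100), and for neither does it show change over time. The counts remain valid and match the declared endpoint, so this is a cheap improvement in reporting and not a correction of an invalid analysis.

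**What to change.** Keep n (%) in SAP 9.1 and add the following.

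- **Main addition, any TEAE.** By year since first dose in GLYX13-C-203, labelled that way, give the number entering the year, the subject-years followed in it, and the number and percent with a TEAE starting in it, whether or not they had one before.
- **TESAEs and TEAEs leading to discontinuation.** Give first-onset counts by year, with the number at risk at the start of each.
- **Secondary addition.** Give subjects with a first event per 100 subject-years at risk, from first dose to the earliest of first event, last dose + 30 days, or study exit. Show it only next to the by-year table. For TEAEs leading to discontinuation, state the end of time at risk that is used: 30 days after stopping is about 16% of a 0.5-year stay (0.082/0.5), and a subject already off drug can no longer have this event.
- **Counting rules.** State the day cut-offs for each year. State whether a severity change recorded with its own onset date (Protocol 12.7.2) counts as a new onset. State how start dates imputed under SAP 14.8 are handled, for example by flagging them.

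The cost is SAP wording and several descriptive tables from dates already collected, with no new data. The tables should carry their limits: small later cells, part-year follow-up, first-onset figures that fall as higher-risk subjects drop out of the risk set, and selection, since those who leave for adverse events or poor tolerability are not in the later years.

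### The TESAE rule in SAP 9.1 omits AEs that turn serious after dosing, so a serious TEAE that began before the first dose can be missing from the TESAE table

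*SAP*

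**What the plan says.** SAP 9.1 gives three routes to TEAE status. An AE, classified by preferred term, is a "treatment emergent adverse event (TEAE) if it was not present before the first dose of study drug". It also qualifies if it "was present before the date of the first dose of study drug and increased in severity during the study period till the end of participation". Where several pre-dose AEs share the preferred term, "then the AE with the greatest severity will be used as the benchmark for comparison with the AEs occurring during the study". The third route concerns seriousness: "An AE that becomes serious on or after the first dose of study drug will also be considered as TEAE". There is an upper limit in time: "An AE that occurs more than 30 days after the date of the last dose of study drug will not be considered" a TEAE.

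TESAE is then defined separately, by time alone: "An SAE that occurred between the date of the first dose of study drug and 30 days after the date of the last dose", inclusive. This rule does not require TEAE status and does not mention events that become serious. The next sentence adds that "the incidence of on-therapy SAEs that led to death will be summarized separately by preferred term". The available text does not define *on-therapy*. The listings paragraph of SAP 9.1 then calls for listings of all subjects with SAEs, including SAEs from screening, and of all deaths.

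On data collection, Protocol 12.7.1 starts AE recording at consent and ends it 30 days after the last injection. It says: "Each AE will also be described in terms of duration (start and stop date), severity, association with the study drug, action(s) taken, and outcome". Protocol 12.7.2 has a change of severity entered as a separate record with its own onset date. It has no matching rule for a change in seriousness.

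**The concern.** The SAP foresaw the AE that begins before dosing and turns serious afterwards, because its third TEAE route exists for that event. The TESAE rule leaves the route out, so one event can be treatment-emergent and serious and still not be a TESAE.

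Safety is the study's only stated objective, and the TESAE table is where a reader looks for serious events on drug. An event that turns serious during treatment is one that this table should show. The primary endpoint, the number of subjects with an AE, is not altered: the event is an AE and a TEAE either way. What is at stake is the count in the TESAE table and its agreement with the TEAE table.

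**Working it through.** The plan gives no figure to reproduce here, so the check is to apply the rules to each type of event.

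**Inputs.** TEAE and TESAE rules: SAP 9.1. AE and SAE collection from consent to 30 days after last dose: Protocol 12.7.1 and 12.8. New record on a change of severity: Protocol 12.7.2. Maximum of 100 subjects: SAP 12.0.

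**Step 1. Classify the events.** *Occurred* can mean the onset date or the date the event became serious.

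| Event | TEAE? | TESAE if *occurred* = onset | TESAE if *occurred* = date became serious |
|---|---|---|---|
| A. Starts after consent and before the day of first dose; becomes serious on treatment; grade unchanged | Yes, third route | **No** | Yes |
| B. As A, but the grade rises when it turns serious | Yes | Yes; the new record has an on-treatment onset | Yes |
| C. New preferred term, starts on treatment, serious from onset | Yes | Yes | Yes |
| D. Starts on treatment, serious from onset; same term present pre-dose at equal or greater severity | Yes if starting as serious counts as becoming serious; no if only a later conversion counts | Yes | Yes |
| E. Serious from onset on Day 1, before the injection | No | Yes (date rule, inclusive) | Yes |
| F. Starts before first dose; becomes serious more than 30 days after last dose | Yes; the third route has no time limit of its own | No | No |

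Row A is the point. Row B shows its limit. Row F lies largely outside SAE collection. Rows D and E run the other way and are taken up in the verdict.

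**Step 2. Which reading of *occurred* is natural?** Three features point to onset:
- SAP 9.1 uses the same verb for AEs in its 30-day limit, where onset is the plain sense.
- SAP 14.8 imputes only an incomplete start date for AEs.
- Protocol 12.7.1 names a start and a stop date for each AE, and no date of becoming serious.

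**Step 3. Can row A happen?** Pre-dose AEs are recorded from consent. SAP 2.0 allows screening more than 7 days before dosing, provided procedures are repeated. Turning serious without a change of grade is possible: Grade 3 in Protocol 12.7.2 allows for hospitalization without requiring it, and Protocol 12.8 lets an important medical event be serious by judgment.

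**Step 4. Size.** With N subjects in the Safety Population, one omitted subject lowers overall TESAE incidence by 1/N, if that subject has no other TESAE:
- N = 100 (maximum): 1/100 = 1.0 percentage point.
- N = 80 (for illustration): 1/80 = 1.25 percentage points.

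If the subject has another TESAE, the overall incidence does not change. The row for the preferred term still loses that subject unless the other TESAE has the same term. The documents give no rate of pre-dose AEs or of conversion to serious, so the expected number of such subjects cannot be computed.

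**Step 5. After the fix.** If the date of becoming serious governs, row A is a TESAE. If every TESAE counts as a TEAE, no event can be in the TESAE table and absent from the TEAE table.

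**The case against.** The strongest reply is that *occurred* need not mean onset. Where the SAP means onset it can say so: SAP 14.6 and 14.7 speak of AEs that started on or after first dose. Protocol 12.8 defines an SAE by the outcome it results in, so an SAE may be said to occur when that outcome is reached. On that reading row A closes. This stands as a possible reading, but the SAP does not state it, and the features in Step 2 favour onset. Two programmers could produce different tables from the same text.

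Second, the gap is narrow. Grades 1 and 2 in Protocol 12.7.2 involve no or minimal intervention. An AE that leads to hospitalization or becomes life-threatening would therefore usually change grade and gain a new on-treatment record. Row A mostly needs an event already at Grade 3 or above before dosing, in a subject who was still dosed. This stands, and it is why few subjects are expected.

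Third, the date of becoming serious may be obtainable, because Protocol 12.8 requires an SAE report. That is likely but not assured: the minimum report contents in that section are subject identification, reporting source and event outcome.

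Fourth, the listings show every SAE and death. This stands in full. It limits the effect to the incidence tables but does not correct them.

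**Conclusion.** The point holds in a limited form. Under the natural reading, the TESAE rule omits an AE that began between consent and first dose and turned serious on treatment at an unchanged grade, although SAP 9.1 counts that event as a TEAE. The effect is confined to incidence tables. It is 1 percentage point at 100 subjects, slightly more with fewer, for each affected subject with no other TESAE. This rests on *occurred* meaning onset and on at least one such event arising; the documents suggest few.

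A reader might infer more, and the documents do not support it:
- **That TESAEs will often be missing from the TEAE table.** Row D is covered if an SAE starting after dosing counts as one that becomes serious. Row E then remains, and seeing it needs event times. Neither row lowers TESAE incidence, because the event is in that table.
- **That deaths after the last injection will be dropped.** SAP 7.1 ends treatment duration at the last dose, but for exposure; it does not define *on-therapy*. The fatal-event sentence directly follows the TESAE rule and most naturally refers back to it. This is an undefined label.
- **That the tables cannot be reconciled.** With full listings and at most 100 subjects, they can be.
- **That SAE incidence is undercounted by a fifth to a third.** One omission among an assumed 3 to 5 TESAEs would be 1/5 = 20% to 1/3 = 33%, but the documents supply neither that count nor the omission.

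**What to change.** In SAP 9.1:

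1. Define a TESAE as any SAE with onset, or any AE that became serious, from first dose to 30 days after last dose inclusive.
2. State that the date the event became serious governs. For an event serious from the start, this is its onset date.
3. Name the source of that date: the SAE report or a specific eCRF field.
4. State that every TESAE counts as a TEAE.
5. As a minor wording change, describe the fatal-event table as TESAEs with fatal outcome, in place of the on-therapy label.

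The cost is a few SAP sentences and a small change to the table programs. If neither the SAE report nor the eCRF holds the date, sites would need to be queried for the few SAEs that began before first dose.
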